### **1.1.3.2. Notable Immune-Mediated Adverse Reactions of Nivolumab**

Immune-mediated conditions are defined as adverse reactions requiring the use of corticosteroids, with no clear alternate etiology. The most common immune-mediated reactions associated with nivolumab include pneumonitis (including interstitial lung disease), colitis, hepatitis, encephalitis, nephritis and/or renal dysfunction, rash, and endocrinopathies such as hypophysitis, adrenal insufficiency, thyroid disorders, and type 1 diabetes mellitus. The majority of events were moderate or mild; however, severe events were observed, including fatal cases of pneumonitis, fatal limbic encephalitis, and toxic epidermal necrolysis. The onset time of these events is highly variable, ranging from within 1 to 2 days of first dose to more than 2 years after initiation of therapy. In many cases, the events resolved with corticosteroid treatment, and occasional event recurrence was observed after re-initiation of nivolumab therapy.

In fewer than 1% of patients, the following clinically significant immune-mediated adverse reactions occurred: uveitis, iritis, pancreatitis, facial and abducens nerve paresis, demyelination, polymyalgia rheumatica, autoimmune neuropathy, Guillain-Barré syndrome, hypopituitarism, systemic inflammatory response syndrome, gastritis, duodenitis, sarcoidosis, motor dysfunction, vasculitis, and myasthenic syndrome.

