### 5.4.4.2. Treatment Delay

#### 5.4.4.2.1. *Criteria for Treatment Delay*

AGEN2034 administration should be delayed for the following:

- Any Grade  $\geq 2$  non-skin, drug-related AE with the following exceptions:
  - Do not delay treatment for Grade  $\geq 2$  Fatigue and laboratory abnormalities except for:
    - Delay dosing for Grade  $\geq 2$  serum creatinine (more than 1.5x baseline) toxicity
    - If a subject has a baseline AST, ALT, or total bilirubin that is within normal limits, delay dosing for drug-related Grade  $\geq 2$  toxicity;
- Any Grade  $\geq 3$  skin drug-related AE or suspected Stevens-Johnson syndrome (SJS) or toxic epidermal necrolysis (TEN)
- Any Grade  $\geq 3$  drug-related laboratory abnormality with the following exceptions for lymphopenia, AST, ALT, or total bilirubin:
  - Grade 3 lymphopenia does not require a dose delay.
  - If a subject has a baseline AST, ALT, or total bilirubin that is within normal limits, delay dosing for drug-related Grade  $\geq 2$  toxicity.
  - If a subject has baseline AST, ALT, or total bilirubin within the Grade 1 toxicity range, delay dosing for drug-related Grade  $\geq 3$  toxicity.
- Any AE, laboratory abnormality, or inter-current illness which, in the judgment of the investigator, warrants delaying the dose of study drug.

Subjects receiving AGEN2034 who have drug-related toxicities that meet the criteria for dose delay should have treatment delayed until retreatment criteria are met.

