## **5.6. Management of Immune-related Adverse Events**

Immuno-oncology agents such as AGEN2034 are associated with irAEs. Early recognition and management of irAEs may mitigate severe toxicity. Investigators should also monitor subjects closely for potential irAEs, which may manifest at the earliest after weeks of treatment. Such events may consist of persistent rash, diarrhea, colitis, autoimmune hepatitis, pneumonitis, encephalitis, arthritis, glomerulonephritis, cardiomyopathy, or uveitis and other inflammatory eye conditions.

Management Algorithms have been developed to assist investigators in assessing and managing the following groups of irAEs: Gastrointestinal, Pulmonary, Dermatological, Renal, Hepatic, Neurological, and Endocrine among others.

Adverse events (both non-serious and serious) associated with drug exposure and consistent with an immune phenomenon may represent an immunologic etiology. These immune related AEs may be predicted based on the nature of the study drugs, their mechanism of action, and reported experience with immunotherapies that have a similar mechanism of action. An irAE can occur shortly after the first dose or several months after the last dose of study drug. Particular attention should be paid to AEs that may be suggestive of potential irAEs as outlined below.

Immune-related AEs are considered are considered AESIs and should be reported to the Sponsor per [Section 7.2.2.2](#).

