Unless otherwise stated, the number of subjects with an event (subject-wise) and the number of events (event-wise) will be provided for each summary.

Immune-related AEs will be tabulated using investigator-reported irAEs. .

Infusion related AEs will be tabulated using infusion-related reactions as reported by the investigators.

The following summaries by either SOC and PT or by PT and by toxicity grade will be provided. Summaries will be sorted by decreasing incidence of PT (within SOC, if applicable).

- TEAEs by SOC and PT, and by PT
- TEAEs by relationship to study drug, toxicity grade, SOC, and PT
- Drug-related TEAEs by SOC and PT, and by PT
- TEAEs leading to permanent treatment discontinuation by PT
- TEAEs leading to death by PT
- Drug-related TEAEs leading to permanent treatment discontinuation by PT
- Drug-related TEAEs leading to death by PT
- Serious TEAEs by SOC and PT, and by PT
- Serious TEAEs by relationship to study drug and toxicity grade, by SOC and PT
- Drug related serious TEAEs by SOC and PT, and by PT
- irAEs by SOC and PT, and by PT
- irAEs by relationship to study drug, toxicity grade, SOC, and PT
- Infusion-related TEAEs by SOC and PT, and by PT
- Infusion-related TEAEs by relationship to study drug, toxicity grade, SOC, and PT
- Laboratory abnormalities worsening (in at least one on-study measurement, relative to baseline) by NCI-CTCAE v4.03 criteria.
- ALT, AST, or bilirubin normal at baseline but with elevations $\geq 2 \times$ ULN.

The overall summary of will be reported by age (age < 55 vs age ≥ 55 , age < 65 vs age ≥ 65 , and age < 75 vs age ≥ 75), by race group including at least 5 subjects (groups < 5 subjects will be reported summarily as “Other”, patients treated in France who did not report race will be summarized as “Not reported (France)”), region (US vs EU vs other), and by normal vs abnormal creatinine and bilirubin levels at baseline.

In addition, the overall summary of AE incidence per month of drug exposure will be presented. Such a summary will report #patients/(total time of exposure in months) and #AEs/(total time of exposure in months.)

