The analysis of irAEs in the above summaries will be performed using data as reported by investigator (the primary analysis). In addition, as an exploratory analysis, TEAEs using sponsor's broad and narrow definitions of irAEs, will be summarized. For each irAE, the summary will include median time (and range) to onset, median duration (and range) of the first instance of such AE per patient. Finally, descriptive statistics will be provided for time of onset, cycle of onset, and cumulative dose at onset of first irAE of any type.

If an SOC or PT was reported more than once for a subject, the subject would only be counted once in the incidence for that SOC or PT.

In tabulation by severity grade:

- For a given SOC, only the most severe SOC for each subject will be included
- For a given PT, only the most severe PT for each subject will be included

In addition, TEAEs (evaluated within extended treatment period) will be reported for the following clusters of immune-mediated AEs: pneumonitis, colitis and diarrhea, hepatitis, and liver function abnormalities, endocrinopathies, nephritis and renal dysfunction, skin disorders, other immune-related AEs. These clusters will be defined by the following MedDRA version 22.1 Preferred Terms:

- **Pneumonitis:** interstitial lung disease; pneumonitis; acute interstitial pneumonitis; immune-mediated pneumonitis
- **Colitis:** allergic colitis, autoimmune colitis, colitis, colitis erosive, colitis microscopic, enterocolitis hemorrhagic, eosinophilic colitis, necrotizing colitis, neutropenic colitis, enterocolitis, immune-mediated enterocolitis,
- **Diarrhea:** diarrhoea, diarrhoea hemorrhagic
- **Hepatitis:** acute hepatic failure, autoimmune hepatitis, hepatic failure, hepatitis, hepatitis acute, hepatotoxicity, liver injury, hepatocellular injury, immune-mediated hepatitis, immune-mediated hepatic disorder, drug-induced liver injury
- **Hypothyroidism:** autoimmune hypothyroidism, hypothyroid goiter, hypothyroidism, immune-mediated hypothyroidism, myxoedema, thyroid atrophy
- **Hyperthyroidism:** Basedow's disease, hyperthyroidism, Marine Lenhart syndrome, primary hyperthyroidism, immune-mediated hyperthyroidism, secondary hyperthyroidism, tertiary hyperthyroidism, thyroid dermatopathy, thyroid crisis, thyrotoxic periodic paralysis, toxic goiter, toxic nodular goiter,

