- **Thyroiditis:** autoimmune thyroiditis, thyroiditis, thyroid acute, thyroiditis chronic, thyroiditis fibrous chronic, thyroiditis subacute, immune-mediated thyroiditis

- **Neuroendocrine Disorders (Pituitary-Adrenal insufficiency):** Addison's disease, adrenal androgen deficiency, adrenal insufficiency, adrenal suppression, adrenocortical insufficiency acute, glucocorticoid deficiency, hypoaldosteronism, mineralocorticoid deficiency, hypophysitis, lymphocytic hypophysitis, hypopituitarism
- **Diabetes** without prior history: type 1 diabetes mellitus, diabetes mellitus, latent autoimmune diabetes in adults, diabetic ketoacidosis.
- **Nephritis:** autoimmune nephritis, lupus nephritis, nephritis, nephritis hemorrhagic, immune-mediated nephritis
- **Rash:** pemphigoid, rash, rash erythematous, rash generalized, rash macular, rash maculopapular, rash pruritic, rash papular, immune-mediated dermatitis
- **Pruritus:** pruritus, pruritus allergic, pruritus generalized

Other Immune-related AEs: myocarditis, immune-mediated myocarditis, uveitis, immune-mediated uveitis, iritis, vitiligo, psoriasis, myositis, immune-mediated myositis, rheumatoid arthritis, systemic inflammatory response syndrome, sarcoidosis, autoimmune disorder, meningitis, encephalitis, encephalitis autoimmune, immune-mediated encephalitis, encephalopathy, autoimmune encephalopathy, immune-mediated encephalopathy, Guillain-Barre syndrome, myasthenia gravis, demyelination, stomatitis, pancreatitis, autoimmune pancreatitis, pancreatitis acute, immune-mediated pancreatitis, immune-mediated gastritis, lichen planus, colitis ulcerative, Crohn's disease, inflammatory bowel disease, hemolytic anemia, immune-thrombocytopenia, immune thrombocytopenic purpura, aplastic anemia, bacytopenia, pancytopenia, immune-mediated pancytopenia

For each cluster, the analysis will summarize: the total incidence and number of all TEAEs included in the cluster and by severity grade, % of pts who received treatment with pituitary and hypothalamic hormones and analogues, with corticosteroids for systemic use, or with thyroid therapy (concomitant medications in, respectively, H01, H02 and H03 ATC2 groups indicated for AE and started following AE onset but no later than the date of AE resolution or 21 days from AE onset, whichever comes earlier), % leading to dose hold, % leading to drug discontinuation, % resolved, time to onset of first TEAE and duration of all TEAEs and TEAEs of grade ≥ 3 .

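### The SAP's immune-mediated AE clusters are closed term lists that leave out immune harms the protocol names, including Stevens-Johnson syndrome and toxic epidermal necrolysis

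*SAP*

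**What the plan says.** SAP 7.6.2 sets out the clusters with the statement "These clusters will be defined by the following MedDRA version 22.1 Preferred Terms". What follows is a series of enumerated lists. The Rash list reads "pemphigoid, rash, rash erythematous, rash generalized, rash macular, rash maculopapular, rash pruritic, rash papular, immune-mediated dermatitis". The last group, Other Immune-related AEs, is also a fixed list and does not collect whatever fits nowhere else. There is no SMQ, no higher-level term and no case-review route.

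For each cluster the SAP reports incidence and grade, treatment with pituitary or hypothalamic hormones, systemic corticosteroids or thyroid therapy, and the percentages "leading to dose hold, % leading to drug discontinuation, % resolved, time to onset of first TEAE", together with duration for all events and for grade 3 or higher events.

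The protocol names immune harms in three places:

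- Section 1.1.3.2 lists severe reactions to nivolumab, including "fatal limbic encephalitis, and toxic epidermal necrolysis". It then gives a sentence of reactions seen in under 1% of patients, which ends "gastritis, duodenitis, sarcoidosis, motor dysfunction, vasculitis, and myasthenic syndrome".
- Section 5.4.4.2.1 makes suspicion of SJS or TEN a reason to delay dosing.
- Section 5.6 tells investigators to watch for events that include "pneumonitis, encephalitis, arthritis, glomerulonephritis, cardiomyopathy, or uveitis and other inflammatory eye conditions".

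Separately, SAP 7.6.2 tabulates investigator-reported immune-related events, for example "irAEs by relationship to study drug, toxicity grade, SOC, and PT". It calls this the primary irAE analysis.

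**The concern.** Because the clusters are closed, an event enters one only if its coded term is on a list. A case of SJS, TEN, vasculitis, polymyalgia rheumatica or autoimmune neuropathy enters none. Arthritis, glomerulonephritis and cardiomyopathy are counted only if coded to a neighbouring listed term.

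No visible rule explains the gaps. Rarity does not, since Marine Lenhart syndrome and thyrotoxic periodic paralysis are listed. Specificity does not, since rash, diarrhoea, stomatitis and encephalopathy are listed. The skin terms run from pruritus to pemphigoid but omit the two severe skin reactions that the protocol singles out.

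At stake is the completeness of a safety summary. The clusters are the only immune grouping whose terms the SAP spells out and that does not depend on the investigator's irAE flag. The sponsor's broad and narrow irAE definitions are mentioned in 7.6.2, but the SAP gives no terms for them.

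**Working it through.** **1. The plan's own safety figure.** SAP 7.1 states at least a 77% probability of seeing an AE with a true rate of 1% or more in 150 subjects. P(at least one) = 1 − (1 − p)^n = 1 − 0.99^150 = 0.779. This reproduces the stated figure.

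**2. Protocol harms against the SAP lists.** All 125 terms in the cluster lists were searched.

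| Harm named in the protocol | Protocol section | Term in any SAP cluster |
|---|---|---|
| SJS | 5.4.4.2.1 | none |
| TEN | 1.1.3.2, 5.4.4.2.1 | none |
| Vasculitis | 1.1.3.2 | none |
| Polymyalgia rheumatica | 1.1.3.2 | none |
| Autoimmune neuropathy | 1.1.3.2 | none |
| Duodenitis | 1.1.3.2 | none |
| Motor dysfunction | 1.1.3.2 | none |
| Facial and abducens nerve paresis | 1.1.3.2 | none |
| Gastritis | 1.1.3.2 | immune-mediated gastritis only |
| Myasthenic syndrome | 1.1.3.2 | myasthenia gravis only |
| Arthritis | 5.6 | rheumatoid arthritis only |
| Glomerulonephritis | 5.6 | nephritis terms only |
| Cardiomyopathy | 5.6 | myocarditis terms only |

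**3. Count for the under-1% sentence in protocol 1.1.3.2.** It names 16 reactions, with facial and abducens nerve paresis counted as one. Eight are listed by name: uveitis, iritis, pancreatitis, demyelination, Guillain-Barré syndrome, hypopituitarism, systemic inflammatory response syndrome and sarcoidosis. Two have only a related term and six have none: 8 + 2 + 6 = 16.

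**4. Chance that the gap matters in this trial.** The documents give only an upper bound of 1% for the reactions in that sentence and no rate for SJS, TEN, arthritis or cardiomyopathy. The combined true rate p of the omitted events is therefore an assumption, shown over a range with n = 150.

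| Assumed p | Expected cases, 150 × p | P(at least one) = 1 − (1 − p)^150 |
|---|---|---|
| 0.1% | 0.15 | 13.9% |
| 0.25% | 0.375 | 31.3% |
| 0.5% | 0.75 | 52.9% |
| 1% | 1.5 | 77.9% |

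**5. Where an SJS case would appear.**

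- In the TEAE tables by Preferred Term, the serious TEAE tables if serious, the discontinuation and death tables if applicable, and the listings.
- If flagged as immune-related, also in the irAE tables with grade, time to onset and duration.
- In no cluster. It would be missing from systemic steroid or hormone treatment, percentage with dose hold, percentage resolved, and duration of grade 3 or higher events, which the SAP specifies by cluster only.
- If not flagged, in no immune-specific summary whose terms the SAP gives.

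**The case against.** The clusters are supplementary. The primary irAE analysis uses investigator reports and is open-ended, so any event the investigator suspects is immune-mediated counts. The protocol promises no clusters, so no commitment is broken. An unflagged case is also less likely than it may seem: protocol 7.1.8 has possible immune events worked up and presumes an immune cause when no other is found. Protocol 7.1.1 requires Grade 4 and 5 events to be reported as serious, apart from Grade 4 laboratory abnormalities that meet no seriousness criterion. With at most one or two cases, a percentage with dose hold or a median duration says little more than the individual listing. Finally, unspecific terms such as arthritis and cardiomyopathy would bring in non-immune cases.

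Most of this stands, and it limits the importance of the point: no case is lost to the report. It does not remove the gap. Even a flagged SJS or TEN case would be absent from the cluster-only summaries, and the clusters serve as the check that does not depend on the flag. The specificity argument has some force for arthritis and cardiomyopathy, but it cannot account for leaving out SJS, TEN or vasculitis from lists that already contain rash and diarrhoea.

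**Conclusion.** The concern holds. The cluster rule is explicit and closed. It has no term for SJS, TEN or 6 of the 16 reactions in the under-1% sentence of protocol 1.1.3.2, and only neighbouring terms for arthritis, glomerulonephritis and cardiomyopathy. The finding on the lists needs no assumption. The practical size does: between 0.15 and 1.5 omitted cases expected, or a 14% to 78% chance of at least one, if 150 subjects are treated and the combined true rate lies between 0.1% and 1%.

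The consequence is an incomplete secondary safety summary. No efficacy estimate, power figure, dosing rule or primary safety table changes. It is a minor point, worth correcting because the correction is easy.

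**What to change.** Before the database is available for analysis, amend the lists in SAP 7.6.2:

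- Add a severe cutaneous cluster with Stevens-Johnson syndrome and toxic epidermal necrolysis.
- Add vasculitis, polymyalgia rheumatica, and autoimmune or immune-mediated neuropathy to Other Immune-related AEs.
- Add glomerulonephritis to Nephritis.
- Add arthritis (preferably an immune-mediated arthritis term) and cardiomyopathy to Other Immune-related AEs.
- Check the lists once against protocol 1.1.3.2, 5.4.4.2.1 and 5.6, and give a reason for any named harm still left out. Duodenitis, motor dysfunction and facial or abducens nerve paresis need either a term or such a reason.

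The exact Preferred Terms should be confirmed in the MedDRA version used, since the documents do not show which immune-mediated terms it contains.

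The cost is a list edit. The events are already collected and coded, and sample size and error rates are unaffected. The one drawback is that unspecific arthritis and cardiomyopathy terms may count a few non-immune cases. Timing matters because SAP section 7 treats analyses designed after the planned ones are complete as post hoc.

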**Table 5: Gastrointestinal Immune-related Adverse Event Management Algorithm**

Gastrointestinal Immune-related Adverse Events		
Severity of Diarrhea/Colitis (NCI CTCAE v4.03)	Management	Follow-Up
Grade 1  Diarrhea: <4 stools/day over baseline.  Colitis: asymptomatic.	
 
Continue AGEN2034 therapy per protocol.
 
Symptomatic treatment
 
	
 
Close monitoring for worsening symptoms.
 
Educate subject to report worsening immediately.
 
Consider symptomatic treatment including hydration, electrolyte replacement, dietary changes (e.g. American Dietetic Association colitis diet), and loperamide
 
If worsens: treat as Grade 2 or 3–4.
 

Grade 2  Diarrhea: 4–6 stools per day over baseline; IV fluids indicated <24 h; not interfering with activities of daily living (ADL).  Colitis: abdominal pain; blood in stool	
 
Delay AGEN2034 therapy per protocol.
 
Symptomatic treatment.
 
	
 
If improves to Grade 1: resume AGEN2034 therapy per protocol.
 
If persists >5 to 7 days or recurs: 0.5–1 mg/kg/day methylprednisolone or equivalent.
 
When symptoms improve to Grade 1, taper corticosteroids over at least 1 month; consider prophylactic antibiotics for opportunistic infections; resume AGEN2034 therapy per protocol.
 
If worsens or persists >3 to 5 days with oral corticosteroids: treat as Grade 3–4.
 

Grade 3 to 4  Diarrhea (Grade 3): ≥7 stools per day over baseline; incontinence; IV fluids ≥24 h; interfering with ADL.  Colitis (Grade 3): severe abdominal pain, medical intervention indicated, peritoneal signs.  Grade 4: life-threatening, perforation	
 
Discontinue AGEN2034 therapy per protocol.
 
1–2 mg/kg/day methylprednisolone IV or equivalent.
 
Add prophylactic antibiotics for opportunistic infections.
 
Consider lower endoscopy.
 
	
 
If improves: continue corticosteroids until Grade 1, then taper over at least 1 month.
 
If persists >3 to 5 days, or recurs after improvement: add infliximab 5 mg/kg (if no contraindication). Note: infliximab should not be used in cases of perforation or sepsis.
 

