**Table 7: Hepatic Immune-related Adverse Event Management Algorithm**

Hepatic Immune-related Adverse Events		
Grade of Liver Test Elevation (NCI CTCAE v4.03)	Management	Follow-Up
Grade 1 AST or ALT >ULN to 3 x ULN and/or total bilirubin >ULN to 1.5 x ULN.	
 
Continue AGEN2034 therapy per protocol.
 
	
 
Continue liver function tests (LFT) monitoring per protocol.
 
If worsens: treat as Grade 2 or Grade 3–4.
 

Grade 2 AST or ALT >3 to ≤5 x ULN and/or total bilirubin >1.5 to ≤3 x ULN.	
 
Delay AGEN2034 therapy per protocol.
 
Increase frequency of monitoring to every 3 days.
 
If subject has concurrent AST or ALT > 3 x ULN AND total bilirubin > 2 x ULN, Discontinue AGEN2034 therapy per protocol.
 
	
 
If returns to baseline: resume routine monitoring; resume AGEN2034 therapy per protocol.
 
If elevations persist >5 to 7 days or worsen: 0.5–1 mg/kg/day methylprednisolone IV or oral equivalent. When LFT returns to Grade 1 or baseline, taper corticosteroids over at least 1 month, consider prophylactic antibiotics for opportunistic infections, and resume AGEN2034 therapy per protocol.
 

Grade 3–4 AST or ALT >5 x ULN and/or total bilirubin >3 x ULN.	
 
Discontinue AGEN2034 therapy per protocol.
 
Increase frequency of monitoring to every 1–2 days.
 
1–2 mg/kg/day methylprednisolone IV or oral equivalent*.
 
Add prophylactic antibiotics for opportunistic infections.
 
Consult gastroenterology.
 
Consider obtaining MRI/CT scan of liver and liver biopsy if clinically warranted.
 
	
 
If returns to Grade 2: taper corticosteroids over at least 1 month.
 
If does not improve in > 3 to 5 days, worsens or rebounds: add mycophenolate mofetil 1 g twice daily. If no response within an additional 3–5 days, consider other immunosuppressants per local guidelines.
 

\*The recommended starting dose for Grade 4 hepatitis is 2 mg/kg/day methylprednisolone IV.

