**Table 8: Endocrine Immune-related Adverse Event Management Algorithm**

Endocrine Immune-related Adverse Events		
Endocrine Disorder	Management	Follow-Up
Asymptomatic thyroid-stimulating hormone (TSH) abnormality	
 
Continue AGEN2034 therapy per protocol.
 
If TSH < 0.5 x lower limit of normal (LLN) or TSH > 2 x ULN, or consistently out of range in 2 subsequent measurements: include free thyroxine (fT4) at subsequent cycles as clinically indicated; consider endocrinology consult.
 
	
Symptomatic endocrinopathy	
 
Evaluate endocrine function.
 
Consider pituitary scan.
 
Symptomatic with abnormal lab/pituitary scan: delay AGEN2034 therapy per protocol; 1-2 mg/kg/day methylprednisolone IV or oral equivalent; initiate appropriate hormone therapy.
 
No abnormal lab/ pituitary MRI scan but symptoms persist: repeat labs in 1-3 wk/MRI in 1 month.
 
	
 
If improves (with or without hormone replacement): taper corticosteroids over at least month and consider prophylactic antibiotics for opportunistic infections.
 
Resume AGEN2034 therapy per protocol.
 
Subjects with adrenal insufficiency may need to continue corticosteroids with mineralocorticoid component.
 

Suspicion of adrenal crisis (e.g., severe dehydration, hypotension, shock out of proportion to current illness)	
 
Delay or discontinue AGEN2034 therapy per protocol.
 
Rule out sepsis.
 
Stress dose of IV corticosteroids with mineralocorticoid activity.
 
IV fluids.
 
Consult endocrinologist.
 
If adrenal crisis ruled out, treat as above for symptomatic endocrinopathy.
 
	

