**Table 13: Phase 2 — Schedule of Assessments and Procedures**

	Screening	Treatment Phase (2-week cycles)						End of Treatment		Follow Up 			Survival Follow	
		Cycle 1		Cycle 2		Every Subsequent Odd Cycle	Every Subsequent Even Cycle	Discontinuation Visit	Safety Visit	Visit 1	Visit 2	Visits 3 and 4		
Visits Schedule (days)		1	2	8	1	2	8	1	1	At Discontinuation	4 w from last dose	3 m from last	6 m from last	3 m from last visit
Schedule Window (days) 		-3/+1		-3/+1			-3/+1	-3/+1		≤ 7	± 7	± 7	± 7	
Administrative Procedures	< -42 days													
Informed consent	X													
Review of inclusion / exclusion criteria	X	X												
Issue Emergency Medical Support and Subject Card	X													
Review of medical history and demographics	X													
Review of baseline symptoms	X	X												
Review of prior and concomitant medications	X	X	X	X	X	X	X	X	X	X	X	X	X	
Cancer disease details and prior treatment	X													
Subsequent antineoplastic therapy status									X	X	X	X	X	
Survival status														X
Clinical Procedures / Assessments	< -7 days													
Review AEs 		X	X	X	X	X	X	X	X	X	X	X	X	X
Full Physical Examination	X									X				
Focused Physical Examination		X				X	X	X		X	X	X	X	X
Vital Signs and Weight	X	X			X	X	X	X	X	X	X	X	X	X
12-lead ECG 	X	X		X		X	X	X	X	X	X			
Expanded ECG Evaluation 6a		X	X					See 6a						
ECOG Performance Status	X	X	X	X	X	X	X	X	X	X	X	X	X	X
Biopsy & Imaging Assessments	< -21 days													
Tumor Biopsy 	X							See 						
Tumor Imaging 	X		Every 6 weeks (± 3 days) from first dose until discontinuation of study drug											
Brain Imaging 	X													
Blood Samples for PK, ADA, Biomarkers, and			See Table 14 and Laboratory Manual											

Continued on next page

	Screening	Treatment Phase (2-week cycles)						End of Treatment		Follow Up 			Survival Follow	
		Cycle 1		Cycle 2		Every Subsequent Odd Cycle	Every Subsequent Even Cycle	Discontinuation Visit	Safety Visit	Visit 1	Visit 2	Visits 3 and 4		
Visits Schedule (days)		1	2	8	1	2	8	1	1	At Discontinuation	4 w from last dose	3 m from last	6 m from last	3 m from last visit
Schedule Window (days) 		-3/+1		-3/+1			-3/+1	-3/+1	≤ 7	± 7	± 7	± 7	± 7	
Local Laboratory Procedures / Assessments 	< -7 days													
Core serum chemistry 				X			X	X						

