Full serum chemistry 	X								X	X	X			
Hematology tests 	X		X	X			X	X	X	X	X			
Coagulation tests 	X			X			X		X	X	X			
Endocrine function tests 	X			X			X		X	X	X			
Urinalysis 	X			X			X		X	X	X			
Serum pregnancy test	X 													
Urine pregnancy test		X 					X		X	X	X			
Study drug administration 														
AGEN2034			X		X		X	X						

Abbreviations: ADA: anti-drug antibody; AEs: Adverse Events; d: day; ECG: electrocardiogram; ECOG: Eastern Cooperative Oncology Group; IERC: Independent Endpoint Review Committee; m: month; PBMC: peripheral blood mononuclear cell; PGx: pharmacogenomics; PK: pharmacokinetics; w: week.

Note: Where applicable, assessments performed prior to treatment unless otherwise indicated.

 All subjects who discontinue treatment will have at least one Follow-up Visit at 3 months (± 7 days) after last dose of study drug. Subjects who discontinue due to disease progression and/or start of a new line of therapy will then end participation in the trial. Subjects who received the maximum administrations of the combination of AGEN2034; who have achieved a complete response (CR) according to RECIST 1.1; or who have discontinued treatment due to reasons other than disease progression and/or start of a new line of therapy will be in Follow-up for up to approximately 12 months after last dose of study drug or until disease progression and/or start of a new line of therapy. Every effort should be made to collect subject information on the start of new antineoplastic therapy, disease progression and death.

 After the first Follow-up Visit, subjects that present(ed) with progressive disease and/or start new line of therapy will move into Survival Follow-up and should be contacted by telephone every 2 months for up to 12 months after last dose of study drug to assess for survival status. Post-study treatments and the subject's response to them will also be collected.

 Treatment administration and associated procedures for that visit may be delayed for treatment related AEs beyond the window and subsequent schedule adjusted accordingly.

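### The SAP's 21-day cap on counting treatment of clustered immune-mediated AEs may understate the percent treated, mainly for thyroid therapy, by an amount the documents cannot fix

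*SAP*

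**What the plan says.** SAP Section 7.6.2 defines clusters of immune-mediated AEs by preferred term and evaluates them over the extended on-treatment period, which SAP Section 5.4 runs to 90 days after the last dose or end of study. Among the items summarised per cluster is the percentage of patients treated. It is limited to concomitant medications in the "H01, H02 and H03 ATC2 groups indicated for AE" that were "started following AE onset but no later than the date of AE resolution or 21 days from AE onset, whichever comes earlier". The other items in that sentence (incidence, grade, dose hold, discontinuation, resolution, time to onset, duration) carry no 21-day limit. For duration, unresolved events are followed to the end of the extended period.

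In Protocol Table 13 (Phase 2, 2-week cycles) the row "Endocrine function tests" is marked for subsequent odd cycles and left blank for even ones. Its footnote puts both TSH and free T4 in the panel.

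Protocol Table 8 keeps study drug going for an asymptomatic TSH abnormality. Further work-up follows either a single value beyond set limits or a TSH "consistently out of range in 2 subsequent measurements: include free thyroxine (fT4) at subsequent cycles as clinically indicated". A symptomatic endocrinopathy with an abnormal laboratory result or scan goes to steroid and hormone therapy with no waiting step.

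**The concern.** The cluster table is followed for months because these toxicities can come late, yet the treatment item alone closes three weeks after onset. Thyroid disease is where this matters most plausibly: it is monitored about every four weeks, and one branch of the endocrine algorithm looks to later measurements. A patient whose hypothyroidism is dated to one scheduled test and treated after the next would appear as untreated. An unlabelled percentage will be read as the share of patients who ever needed treatment for the event, and this table feeds the BLA Filing analysis (SAP Section 4.2). An understated share would make the toxicity look less burdensome than it was.

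**Working it through.** The documents give no expected percent treated and no onset-to-treatment delay, so there is no planned figure to reproduce. What can be checked is the test schedule against the cap.

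**Inputs.** Cap: 21 days from AE onset (SAP 7.6.2). Cycle length: 14 days; endocrine panel at odd cycles; visit window −3/+1 days; laboratory samples up to 48 hours before a visit (Protocol Table 13 and footnotes). The table's columns are broken in the text as read; the early mark is taken as Cycle 2 Day 1.

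**Step 1: interval between scheduled thyroid tests.** Odd-cycle Day 1 visits from Cycle 3 fall on days 29, 57, 85, 113, so the interval is 2 × 14 = 28 days.
- Shortest: 28 − 1 (first visit late) − 3 (second visit early) − 2 (second sample drawn ahead) = 22 days.
- Longest: 28 + 3 + 1 + 2 = 34 days.

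Two consecutive scheduled tests from Cycle 3 are therefore always more than 21 days apart. The early tests (days 15 and 29) are closer.

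**Step 2: interval to the next cycle visit.** By the same arithmetic on 14 days: 14 − 1 − 3 − 2 = 8 to 14 + 3 + 1 + 2 = 20 days. Without a dose delay, this is always inside the cap.

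**Step 3: share of treated thyroid events missed, by assumed delay.** The share is P(start − onset > 21). Where onset is taken as uniform between tests, U is the time from the last test to onset, uniform on 0 to 28.

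| Assumption | Delay (days) | Missed |
|---|---|---|
| Treated at symptomatic onset | 0 | 0% |
| Onset at first abnormal test, treated at next cycle | 14 | 0% |
| Onset uniform between tests, treated at next scheduled test | 28 − U | P(U < 7) = 7/28 = 25% |
| As above, plus 14 days | 42 − U | P(U < 21) = 21/28 = 75% |
| Onset at first abnormal test, treated at next scheduled test | 28 | 100% |
| Onset at first abnormal test, treated after two further tests | 56 | 100% |

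**Step 4: effect on the table.** Reported percent = uncapped percent × (1 − share missed). With purely assumed counts of 12 patients with hypothyroidism and 8 treated, and those 12 as denominator, the uncapped figure is 8/12 = 67%. The capped figure is 8/12 (67%) at 0% missed, 6/12 (50%) at 25%, 2/12 (17%) at 75% and 0/12 at 100%.

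**Step 5: steroid waiting steps.** Persistence before steroids is 1 to 2 weeks for Grade 1–2 rash (Table 4) and 5 to 7 days for Grade 2 diarrhoea/colitis (Table 5) and Grade 2 hepatic events (Table 7). Grade 2–3 renal events have no wait (Table 9). All fall inside 21 days unless the event recurs or worsens later.

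**Step 6: partial dates.** If the rules of SAP Sections 5.6 and 5.7 are carried into this item, a medication start with a missing day moves to the first of the month (or the day before first dose in the first dosing month). It can then precede onset and fail the count. Partial AE onsets are also set early, which shortens the window. Both can add to the undercount.

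**The case against.** The strongest reply is that the 21 days run from AE onset, not from the first abnormal TSH. Protocol Section 7.1.2 keeps abnormal laboratory findings out of AE reporting unless they are symptomatic, lead to discontinuation or are judged medically important, and the hypothyroidism cluster lists clinical terms, not a raised TSH. An asymptomatic abnormality will often have no onset date yet. Table 8's asymptomatic branch names no hormone treatment, a single value beyond the limits is also a trigger, free T4 is already in the panel, and symptomatic cases have no wait. All of this stands. A reader might infer that the percentage is too low by construction, or that thyroid replacement cannot be counted; the documents do not support either.

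Two further inferences also fail. One is that steroids for pneumonitis are lost because Grade 1 cases are re-imaged no sooner than every 3 weeks. Table 6 also asks for symptom checks every 2 to 3 days and defines Grade 2 by symptoms, so imaging does not set the timing. The other is that infliximab and mycophenolate would appear nowhere. They lie outside the three drug groups, but SAP Section 7.5.5 summarises and lists all concomitant medications, and in Tables 5 and 7 they are added after steroids, so those patients can already count as treated.

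The window may also serve a purpose. The eCRF is not in the documents, and being indicated for an AE may not tie a drug to one AE record. In a long unresolved event, simply deleting the cap could credit steroids given for something else. That argues for showing both figures. It does not justify reporting the capped one alone and unlabelled.

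**Conclusion.** The point holds as a possible understatement. The cap is one-sided, so compared with the share ever treated for the event it can only leave the percentage equal or lower it. It sits badly with clusters followed to 90 days after the last dose and with scheduled thyroid tests 22 to 34 days apart from Cycle 3. Thyroid therapy is most exposed, then events that worsen or are treated late; most steroid starts that follow the algorithms are not.

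The size is undetermined: 0% to 100% of treated thyroid events, resting wholly on the assumed delay and on how sites date onset. The percentage is correct for its written definition; the risk is that it is read as ever treated. The consequence is confined to one descriptive safety item. The primary endpoint, sample size, AE incidence and investigator-reported irAE analysis are untouched.

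**What to change.** In SAP Section 7.6.2, report for each cluster the percentage of patients with H01, H02 or H03 treatment indicated for the AE and started from onset to resolution, or to the end of the extended on-treatment period if unresolved. Link it to the specific AE where the eCRF allows. Keep the present figure as a second column labelled *started within 21 days of onset*. State the denominator, and say how partial start and onset dates are handled for this item. A separate row for non-steroid immunosuppressants is optional.

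The cost is about one SAP sentence and a little more programming on concomitant medication data already collected. Protocol Section 6.4.1.8.2 continues recording after the Safety Follow-up Visit for reportable SAEs and AESIs, so late treatment of a cluster event reported as neither may be missing. The percentage may become less favourable. In long unresolved events the uncapped column may credit treatment given for another AE, which is why both columns should be shown.
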